#### **Statistical Methods:**

We reported that the average IEFND in the distal leg in T1DM subjects (mean disease duration of 27 years) was 2.2 fibers/mm. We assume that the targeted diabetic subjects have the average IENFD for ages 20-29 shown by published normatives at the start of their disease, and the decline due to diabetes is 10 fibers/mm or an average of 0.25 fibers/mm/year. If the decline is more rapid as neuropathy progresses, then the average decline in IEFND may be as high as 0.5 fibers/mm/year. Based on our assumption about the mechanism by which salsalate will influence IEFND (reduction of inflammation), and published effect of other interventions, we believe that an increase of 1.65 fibers/mm (0.25 + 1.4 = 1.65) in fiber density is possible with treatment with salsalate. The standard deviation

of the change is approximately 2 fibers/mm. With 25 subjects per group there will be 81% power to reject the null hypothesis of no difference between groups using a two-tailed t-test at a 5% level of significance. No formal interim analysis for stopping for efficacy benefit or futility is planned, given the projected duration of follow-up required for the assessment of the primary endpoint. Rather, safety will be assessed periodically and reviewed by a Data and Safety Monitoring Board.

A general linear model will be fitted to the change in IENFD score with factors for treatment group, baseline HbA1c ( $\leq 8.0$  or  $> 8.0\%$ ), and baseline IEFND as fixed covariates. If the distributional assumptions are not met, transformations of IENFD or the use of nonparametric methods will be employed. Sensitivity analyses will be performed to assess how subjects who withdrew may affect conclusions of the analysis. An intent-to-treat analysis set (including subjects who are randomized, treated and have a baseline IENFD) will be used to assess treatment effects with multiple imputation methods employed to impute outcomes for subjects with missing post-baseline data.

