### 3. TRIAL DESIGN

This is a phase II-III, multi-site randomized, double-blind, placebo-controlled clinical trial to evaluate the effect of salsalate on measures of small fiber neuropathy in 70 subjects with T1DM and mild DN. In the original study design we proposed to randomize up to 60 subjects in a 1:1 fashion to up to 3 grams of salsalate or matched placebo. In August 2017 the protocol was modified by recommendation of the DSMB to address differential study medication discontinuation rates and to increase the number of subjects exposed to study drug. Specifically, the protocol will enroll up to 70 subjects and randomize them in a 3:2 fashion to

salsalate or placebo. All subjects enrolled subsequent to the approval of the revised protocol will be randomized in 3:2 fashion, up to 3 grams per day of salsalate or placebo respectively. Treatment duration will be 12 months. Randomization will be stratified by baseline HbA1c ( $\leq 8.0$  or  $> 8.0\%$ ) and by gender within the HbA1c groups. Subjects will be evaluated every 3 months for a total of 12 months.

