#### **10.1. Sample Size Determination**

The purpose of this clinical trial is to provide the preliminary data necessary to design a larger

multi-site clinical trial. There are two assumptions that are necessary to justify the larger trial. The first is that salsalate will cause an increase in nerve fiber density (re-innervation) and the second is that the natural progression of DN, even with treatment for diabetes, leads to loss of nerve fibers. The primary outcome is an assessment of IENFD at the distal thigh after 12 months of placebo or salsalate treatment.

In the largest study of IENFD, Lauria et al provided a table of median IEFND values in the distal leg as a function of age and gender. In the 20-29 age range the average IEFND was 12.2 fibers/mm with an average decline of 0.1 fibers/mm per year. We reported that the average IEFND in the distal leg in T1DM subjects (mean disease duration of 27 years) was 2.2 fibers/mm. If we assume that our diabetic subjects have the average IENFD for ages 20-29 shown by Lauria et al at the start of their disease, then the decline due to diabetes was 10 fibers/mm or an average of 0.25 fibers/mm /year. If the decline is more rapid as neuropathy progresses, then the average decline in IEFND may be as high as 0.5 fibers/mm/year.

In a study of the effect of physical exercise Smith et al found an increase in the IENFD at the thigh of 1.4 fibers/mm after one year of intervention. Based on our assumption about the mechanism by which salsalate will influence IEFND (reduction of inflammation), we believe that a similar increase in fiber density is possible with treatment with salsalate. In multiple studies that reported a change in IEFND over time (including one of our own studies), the standard deviation of the change was approximately 2 fibers/mm. With the above assumptions, there will be an expected difference of 1.65 fibers/mm ( $0.25 + 1.4 = 1.65$ ) in the change between the two groups at the thigh with a standard deviation of 2.0. With 25 subjects per group there will be 81% power to reject the null hypothesis of no difference between groups using a two-tailed t-test at a 5% level of significance. Prior data are insufficient to perform a power calculation for the distal leg.

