The trial will be considered a success if the primary endpoint demonstrates a significant difference between the two groups and one other secondary endpoint trends in a similar direction. This trial will also be considered a success if there is sufficient evidence to show that IEFND increases with salsalate but is likely to decrease with usual treatment. With 25 subjects per group, the standard error of the estimate will be approximately 0.4 [=2/square root (25)] and therefore the confidence interval for the mean change in each group will be the estimated mean change  $\pm$  0.8 fibers/mm; i.e. an increase of greater than 0.8 fibers/mm with salsalate and an observed decrease with placebo (since the expected decrease with placebo is not expected to be large). With these results, this trial would provide the preliminary data needed for a larger trial to validate the effect of salsalate. Assuming 15-20% attrition rates, 70 subjects will be recruited to attain the necessary 50.

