### Analysis of Primary Outcome:

The primary outcome is change from baseline to 12 months in IENFD at the distal thigh. A general linear model will be fitted to the change in IENFD score with factors for treatment group, baseline HbA1c ( $\leq 8.0\%$  or  $> 8.0\%$ ), and baseline IEFND as fixed covariates. If the distributional

assumptions are not met, transformations of IENFD or the use of nonparametric methods will be employed. Sensitivity analyses will be performed to assess how subjects who withdrew may affect conclusions of the analysis. An intent-to-treat analysis set (including subjects who are randomized, treated and have a baseline IENFD) will be used to assess treatment effects with multiple imputation methods employed to impute outcomes for subjects with missing post-baseline data. Depending on the extent and pattern of missingness, other simpler sensitivity analyses may be used: for example, change from baseline to month 12 for subjects completing the study (completers) may be analyzed using an analysis of variance model. The model will include the same covariates that are included in the primary analysis.

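### The one sensitivity analysis Section 10.2 names for withdrawals (completers) would nearly match standard multiple imputation whether or not dropout is informative, so a delta-adjusted analysis should be prespecified

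*Combined protocol and SAP*

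**What the plan says.** Section 10.2 (Analysis of Primary Outcome) models the 12-month change in IENFD at the distal thigh on treatment, HbA1c stratum and baseline IENFD. The analysis set is everyone randomised and treated who has a baseline value, with "multiple imputation methods employed to impute outcomes for subjects with missing post-baseline data" (Synopsis, Statistical Methods; Section 10.2 says the same). Section 10.2 also commits to sensitivity analyses on the influence of withdrawals. Simpler ones may be chosen once the amount and pattern of missing data are known. One example is given: "change from baseline to month 12 for subjects completing the study (completers) may be analyzed using an analysis of variance model", with the covariates of the primary model.

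No imputation model, auxiliary variable or missing-data mechanism is stated, and no analysis that departs from missing at random is named. Section 10 defers detail to a Statistical Analysis Plan to be finalised before unblinding; no such separate text is among the documents.

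Three other places bear on this:

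- **Table 1 and Section 7.1.1:** skin biopsies are taken at baseline and month 12 only.
- **Section 3:** sample size and allocation were changed in August 2017 "by recommendation of the DSMB to address differential study medication discontinuation rates and to increase the number of subjects exposed to study drug". No rates by arm and no direction are given.
- **Sections 5.2.4 and 6.5:** participants stay in follow-up unless consent is withdrawn or continuing is judged unsafe. Once consent is withdrawn, no more data are collected.

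**The concern.** The promised sensitivity analyses should show whether the result depends on what is assumed about participants without a month-12 biopsy. Standard multiple imputation assumes that a missing participant would have changed like a same-arm participant with the same covariates. A completers model with those covariates assumes the same. With no interim IENFD to separate the two, they should agree even when that assumption is badly wrong.

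At stake is the size of the reported effect. If participants who leave do worse than those who stay, and this differs between arms in frequency or degree, both analyses are biased by the same amount and appear to confirm each other.

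**Working it through.** **1. The plan's own figure.** Section 10.1 gives the inputs: "there will be an expected difference of 1.65 fibers/mm"; "the standard deviation of the change was approximately 2 fibers/mm"; and "With 25 subjects per group there will be 81% power to reject the null hypothesis of no difference between groups". The test is a two-sided t-test at the 5% level. Noncentrality = 1.65 / (2 × √(1/25 + 1/25)) = 1.65 / 0.566 = 2.92 on 48 degrees of freedom. Power = 81.5%, so the stated 81% reproduces.

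**2. Why the two analyses coincide.** Let b be the completers' regression estimate. Imputed values scatter around the prediction from b. Refitting the same regression to observed plus imputed data returns b on average, leaving only the noise of a finite number of imputations. This holds for any dropout mechanism, provided imputation uses only the model's own terms.

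**3. Bias common to both.** Let p be the share of missing biopsies and δ the amount by which missing participants do worse than same-arm completers, for salsalate (S) and placebo (P):

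bias = p_S × δ_S − p_P × δ_P

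The documents give no rates by arm and no δ, so all the values below are assumptions. Allocation is taken as 42:28 (70 at 3:2), although those randomised before August 2017 were allocated 1:1. Section 10.1 says "Assuming 15-20% attrition rates, 70 subjects will be recruited to attain the necessary 50".

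| Missing S / P | Overall | δ = 1 in both arms | δ_S = 1.65, δ_P = 0 | δ_S = 2, δ_P = 0 |
|---|---|---|---|---|
| 20% / 20% | 20% | 0.00 | 0.33 | 0.40 |
| 25% / 10% | 19% | 0.15 | 0.41 | 0.50 |
| 30% / 10% | 22% | 0.20 | 0.49 | 0.60 |
| 40% / 10% | 28% | 0.30 | 0.66 | 0.80 |

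The last two rows exceed the planned 15-20% attrition, but recruiting 70 to retain 50 allows 20/70 = 28.6%. At 25%/10% with salsalate dropouts losing the effect, the all-randomised difference is 1.65 − 0.25 × 1.65 = 1.24.

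**4. Simulation.** 2,000 trials per scenario, SD 2, 20 imputations, the plan's three model terms (HbA1c stratum and baseline were given no true effect):

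| Missing S / P | δ_S / δ_P | True difference | Completers | Multiple imputation | Delta-adjusted, correct δ |
|---|---|---|---|---|---|
| 25% / 10% | 0 / 0 | 1.65 | 1.62 | 1.62 | 1.62 |
| 25% / 10% | 1.65 / 0 | 1.24 | 1.65 | 1.66 | 1.24 |
| 30% / 10% | 1.65 / 0 | 1.16 | 1.66 | 1.66 | 1.16 |
| 20% / 20% | 1.65 / 1.65 | 1.65 | 1.63 | 1.63 | 1.63 |

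Completers and imputation correlate at 0.995 in every scenario. At 25%/10% they differ by about 0.04 on average, with or without bias (standard errors 0.54 and 0.55). The last row shows that equal rates and equal δ produce no bias.

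**5. Tipping point.** For an observed 1.65, shifting salsalate only and holding the completers' standard error fixed, significance is lost at δ = (1.65 − critical difference) / p_S:

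- 15%/15%: (1.65 − 1.060) / 0.15 ≈ 3.9
- 20%/20%: (1.65 − 1.094) / 0.20 ≈ 2.8
- 25%/10%: (1.65 − 1.071) / 0.25 ≈ 2.3
- 30%/10%: (1.65 − 1.089) / 0.30 ≈ 1.9
- 40%/10%: (1.65 − 1.133) / 0.40 ≈ 1.3

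A range that stopped at the design effect of 1.65 would miss the tipping point in all but the last case.

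**6. Within-arm success route.** Section 10.1 also counts as success an increase above 0.8 on salsalate with an observed decrease on placebo. Bias within an arm does not cancel between arms. If salsalate completers average the planned 1.4 and δ_S = 1.65, the arm mean is 1.4 − 0.25 × 1.65 = 0.99 with 25% missing and 1.4 − 0.40 × 1.65 = 0.74 with 40% missing, the latter below the threshold.

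**The case against.** The strongest reply is that Section 3 concerns stopping medication, not missing biopsies. Section 5.2.4 keeps such participants in follow-up, so many would contribute a month-12 biopsy and any loss of drug effect would be observed. This stands as a limit. A reader might infer that the protocol already reports differential dropout, or that the primary estimate is biased; the documents support neither. Nor do they say which arm stopped more often, although the shift of allocation towards salsalate invites a guess. Routes from stopping drug to a missing biopsy do exist: withdrawn consent or safety (Sections 5.2.4 and 6.5), and possible withdrawal after three months without drug (Appendix A). Their frequency is not given.

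Second, missing at random and imputation from the model terms alone are inferences. Imputation could use compliance, laboratory values or month-6 scores from Table 1 and then differ from completers. True, but none is named, and the result would still assume missing at random.

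Third, completers is only an optional example. Section 10.2 makes a general commitment, could be read as treating imputation itself as one of the sensitivity analyses, and leaves a later plan free to add more. It would therefore be too strong to say that completers is the designated test for informative dropout. What stands is that no analysis able to detect the problem is specified.

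Fourth, a reader might infer a loss of power or a false positive. In the scenarios above the planned estimate stays near 1.65, so the planned test does not lose power; what changes is what the estimate describes. If dropouts merely lose the drug effect, the bias is p_S times that effect, which is zero when the drug does nothing. Bias without a drug effect would need another mechanism, such as equally poor outcomes among dropouts in both arms at unequal rates.

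**Conclusion.** The point holds in this form: the two named analyses would nearly coincide whether or not dropout is informative, so their agreement is not evidence of robustness. Under the assumed 25%/10% missing with salsalate dropouts losing the effect, both show about 1.65 against about 1.24, an excess of 0.41 or roughly three quarters of a standard error (0.41 / 0.54). Across the assumed unequal-dropout scenarios, from 25%/10% to 40%/10%, the bias runs from 0.15 to 0.80. It is zero when rates and δ are equal in both arms. These figures rest on assumed rates, assumed δ, a 42:28 split and imputation from the model's own terms. Multiple imputation remains a defensible primary analysis. This is an inexpensive improvement worth making before unblinding, not a demonstration that the result will be wrong.

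**What to change.** In Section 10.2, or in the Statistical Analysis Plan before unblinding:

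- Keep multiple imputation as the primary analysis, and state the imputation model, any auxiliary variables and the assumed mechanism.
- Use as observed data every month-12 biopsy from participants who stopped drug but stayed in follow-up.
- Prespecify a delta-adjusted tipping-point analysis with δ varied separately by arm, for example 0 to −3 fibers/mm, extended if significance has not been lost by then (at 15%/15% missing it takes about −3.9). Reference-based imputation from the placebo arm is an optional addition.
- Apply the same shifts to the within-arm success criterion in Section 10.1.
- Report missing month-12 biopsies by arm and reason.
- Keep the completers model as descriptive only.

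The cost is a few lines of text and a little programming. The sensitivity result may look less favourable than the primary one.

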#### Analyses of Secondary Outcomes:

Due to multiple tests, formal statistical testing won't be performed; p-values will be reported to allow the reader to assess the result. For analysis of repeated measures of continuous data (change from screening/baseline to 12 months in NC studies, quantitative sensory testing, CAN measures, Neuropathy Symptoms, Pain, and NeuroQOL domain scores), a longitudinal approach will be employed. Specifically, each outcome will be analyzed using a mixed effect model for repeated measures with the treatment group and baseline HbA1c ( $\leq 8.0$  or  $> 8.0\%$ ) as fixed covariates. Under the model, time of assessment will be a continuous variable and the outcome will be modeled as a linear function of time. Appropriate non-linear parametric or non-parametric tests may be applied if assumptions of the model are not satisfied.

Logistic regression will be used to compare the proportion of subjects who have confirmed clinical neuropathy with NC and those who had normal NC and therefore required an assessment of IENFD for trial entry, between the salsalate and placebo groups, with covariates for treatment group, and baseline HbA1c ( $\leq 8.0$  or  $> 8.0\%$ ). The components of this composite endpoint will also be assessed. Rank-transformation analysis of covariance will be used on each of the NC values, and an overall treatment group differences in the multiple NC values will be assessed using the nonparametric Wei-Lachin rank test of stochastic order. The impact of additional covariates on the relationship between IENFD and confirmed clinical neuropathy and treatment will be explored by adding age, sex, height, weight, BMI, cigarette smoking, cardiovascular risk factors and concomitant medications into the models described above. A forward stepwise selection procedure will be used, with  $p < 0.10$  used to retain covariates. Interaction terms between treatment groups and select covariates will be investigated. In addition, we will adjust for the effect of changes in glucose on outcomes during the course of treatment by including HbA1c as a time-varying covariate in models.

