### **6.1. Recruitment/Screening**

#### Visit 1: Screening/Eligibility

An eligibility visit will be scheduled for subjects who, based on preliminary screening (telephone, email, medical chart review) meet the general entry criteria (age, T1DM, diabetes duration, symptomatic peripheral neuropathy, no contraindications for salsalate, etc.). At visit 1 the investigator or her designee will obtain written informed consent, after which all required eligibility examinations will be performed. The eligibility examination will include the following laboratory assessments: HbA1c, metabolic comprehensive panel (METCOMP), complete blood count with platelets (CBCP), thyroid stimulating hormone (TSH), lipid profile, cystatin-C, uric acid, urine albumin assessment, and in all women of child bearing age and potential, a urine

pregnancy test, even if an accepted method of contraception is being used. If any of the required laboratory measures are documented in the subject's medical record as being completed in the prior 3 months (1 month for HbA1c, and 6 months for urine albumin), they will not need to be repeated at the screening visit. Additional blood and urine will be obtained for Luminex assays of inflammatory markers. The Luminex assays though may be postponed until the baseline examination.

Weight, height and seated blood pressure and pulse will be obtained.

A structured neurologic history and physical examination and nerve conduction studies will be performed at the screening visit to verify and document the presence of signs or symptoms of peripheral neuropathy, the presence of a sural nerve response, and abnormality of at least one abnormal nerve attribute (amplitude, latency, conduction velocity or f-wave) in the sural, peroneal or ulnar nerve. In the absence of a sural nerve response (e.g., sural amplitude is 0  $\mu$ V, response is unobtainable, then the presence of a peroneal motor nerve conduction velocity of  $\geq$  35 meters per second will be required for inclusion. Quantitative sensory testing will also be conducted at the screening visit.

All visit 1 measures are ideally to be completed within a 4-week time frame but may take up to 6 months (180 days) if repeated measures are needed, and may be done at one, or over several visits if that is more convenient for the subject.

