### **10. DATA ANALYSIS/STATISTICAL METHODS**

Detailed methodology for summary and statistical analyses of the data collected in this trial will be documented in a Statistical Analysis Plan, which will be prepared during the R34 and finalized prior to breaking of the blind.

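### The mixed model for the continuous secondary outcomes omits adjustment for each outcome's own baseline, which costs precision, and leaves the treatment-by-time term and month-12 contrast unstated

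*Combined protocol and SAP*

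**What the plan says.** Section 10.2, under Analyses of Secondary Outcomes, introduces the continuous outcomes as "change from screening/baseline to 12 months in NC studies, quantitative sensory testing, CAN measures, Neuropathy Symptoms, Pain, and NeuroQOL domain scores". It then says that "each outcome will be analyzed using a mixed effect model for repeated measures with the treatment group and baseline HbA1c" (cut at 8.0%) as fixed covariates, and continues: "Under the model, time of assessment will be a continuous variable and the outcome will be modeled as a linear function of time". No other term is listed. The one interaction sentence in the section concerns treatment by selected covariates, in the exploratory covariate step. The text speaks of change as the target but does not say whether the response in the model is the value at each visit or the change.

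The primary model in the same section does state its response (change) and lists treatment, HbA1c stratum "and baseline IEFND as fixed covariates".

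The visit schedule (Sections 2, 6.1 and 7.1.2, Table 1) gives:
- nerve conduction (NC) and quantitative sensory testing (QST): screening and month 12. Screening "may take up to 6 months (180 days) if repeated measures are needed";
- cardiovascular autonomic (CAN) reflex tests: baseline and month 12;
- Neuropathic Pain Scale and NeuroQOL: baseline, month 6 and month 12.

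Three further statements bear on the point. For the secondary outcomes, "Due to multiple tests, formal statistical testing won't be performed", and p-values are given for the reader's information. For nerve conduction, "Rank-transformation analysis of covariance will be used on each of the NC values", without listed covariates. Section 10 leaves detailed methodology to a "Statistical Analysis Plan, which will be prepared during the R34 and finalized prior to breaking of the blind".

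**The concern.** The stated target is a change to month 12, but the model lists nothing that isolates a month-12 difference and does not use the baseline value as a covariate. With no formal testing, the estimate and its interval are what a reader takes from these outcomes. In a trial of 70 subjects those intervals are wide, and baseline is the one strong predictor already collected for every outcome. The protocol uses it for the primary outcome but not here.

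The unstated interaction and contrast raise a second question: would the reported treatment coefficient be the month-12 effect at all?

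**Working it through.** The plan attaches no sample size or precision figure to these outcomes, so there is nothing to reproduce. Its 81% power belongs to the primary outcome. The correlations, effect shapes and numbers analysed below are assumptions.

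**Step 1. Precision without own baseline.** Let ρ be the correlation between baseline and month 12, with equal SDs at both visits. In units of that SD, and with f = √(1/n₁ + 1/n₂):
- comparison of changes: variance f² × 2(1 − ρ);
- ANCOVA on own baseline: variance f² × (1 − ρ²);
- ratio: 2(1 − ρ)/(1 − ρ²) = 2/(1 + ρ).

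At ρ = 0.5 the ratio is 2/1.5 = 1.33; at ρ = 0.7 it is 2/1.7 = 1.18.

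**Step 2. The same holds for slopes.** At visits 0 and 12 the slope times 12 is the change. At visits 0, 6 and 12, with a covariance symmetric in time (compound symmetry or AR), the month-6 value gets zero weight. So 12 × slope is again the month-12 value minus the baseline value, with the variance of the change comparison.

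**Step 3. Interval widths.** Take 70 subjects, 3:2 allocation and 80% retained: 70 × 0.6 × 0.8 = 33.6, so 34; 70 × 0.4 × 0.8 = 22.4, so 22. Then f = √(1/34 + 1/22) = 0.274.

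| ρ | Change or slope: 1.96·f·√(2(1−ρ)) | ANCOVA: 1.96·f·√(1−ρ²) |
|---|---|---|
| 0.5 | 0.54 SD | 0.46 SD |
| 0.7 | 0.42 SD | 0.38 SD |

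With 25 versus 25 the pairs are 0.55 versus 0.48 and 0.43 versus 0.40. Put another way, 56 subjects analysed without own baseline carry the information of 56 × 0.75 = 42 (ρ = 0.5) to 56 × 0.85 = 48 (ρ = 0.7) analysed with it.

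**Step 4. What the treatment coefficient estimates.** Let D be the true month-12 difference, with none expected at baseline. In a model with treatment and time as main effects only, the treatment coefficient is a weighted average of the visit differences, with weights w = V⁻¹1/(1′V⁻¹1), where V is the covariance of the visits.
- Visit values including baseline, visits 0/12, equal variances: weights 0.5 and 0.5, so 0.5 × 0 + 0.5 × D = 0.50 D. Visits 0/6/12 with linear build-up also give 0.50 D.
- Change scores, one follow-up: 1.00 D.
- Change scores at months 6 and 12, linear build-up: compound symmetry gives weights 0.5/0.5, so 0.5 × 0.5 + 0.5 × 1 = 0.75 D. AR gives weights 0.85/0.15 (ρ = 0.5) and 0.92/0.08 (ρ = 0.7), so 0.57 D and 0.54 D. If the full effect is present by month 6, the share is 1.00.
- Treatment-by-time included and slopes compared, at nominal visit times: 12 × the slope difference is 1.00 D by step 2.

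A simulation of the two-visit case supports this: 4000 runs, 34 versus 22, screening up to 6 months before Day 0, true effect 0.6 SD, ρ = 0.5/0.7. The mean estimates were 0.299/0.303 on visit values, 0.600/0.597 on changes with elapsed time as a covariate, and 0.600/0.599 for ANCOVA.

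**The case against.** The strongest reply is that the text is most naturally read as a slope comparison: it describes a longitudinal approach, a change target and a linear time trend. On that reading the treatment-by-time term is merely unwritten, and the SAP would normally supply it. This stands. A reader might infer that the plan will report half the month-12 effect and that a later trial sized on it with the same SD would need four times the subjects (1/0.50²). The documents do not support that. It requires visit values as the response, no interaction, and the main effect reported as the month-12 effect, and none of these is stated. Nor does anything say that the larger trial would be sized on a secondary coefficient; the two assumptions that Section 10.1 names for it concern nerve fibre density.

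A reader might also infer that the trial's success rule is at risk. It is essentially unaffected: beyond a significant primary result it asks only that one secondary endpoint trend the same way.

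Other provisions help only in part. Section 10.2 refits models with variables that differ significantly at baseline, and allows non-linear or nonparametric methods if model assumptions fail. Both are conditional, and neither is a planned own-baseline adjustment. The rank ANCOVA covers nerve conduction only.

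Finally, it can be said that omitting baseline costs precision, not bias. That is true on the change and slope readings, and it is the loss claimed here.

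**Conclusion.** The concern holds as a modest loss of precision plus an incomplete specification. On the change and slope readings alike, leaving out own baseline raises the variance of the month-12 comparison by 18% to 33%, for assumed correlations of 0.7 to 0.5 and equal SDs at the two visits. The loss is larger if the correlation is lower. The split of 34 versus 22 is also assumed, because 3:2 allocation applies only to subjects enrolled after the August 2017 change.

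Understatement of the month-12 effect is conditional on a literal fit without interaction: about 0.50 on visit values; on change scores, 1.00 with one follow-up and about 0.54 to 0.75 for months 6 and 12 with linear build-up.

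This is a low-severity improvement that costs nothing in data. The outcomes are secondary and not formally tested, and the primary analysis is unaffected.

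**What to change.** State the following in Section 10.2 or in the SAP, before unblinding:
- **One follow-up (NC, QST, CAN reflex tests):** ANCOVA of the month-12 value on treatment, the outcome's own screening or baseline value, and the randomisation strata. List the covariates of the nerve conduction rank ANCOVA in the same way. Section 3 names gender within HbA1c group as a stratum while Section 5.1 names HbA1c only, so the strata actually used should be given.
- **Several follow-ups (pain, NeuroQOL):** a mixed model with treatment-by-visit, and either own baseline as a covariate or baseline as a response with equal arm means.
- **All:** the month-12 treatment contrast with its 95% CI as the reported estimate.

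The cost is a few sentences and a few model parameters; the baseline values are already collected.

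A separate point to reconcile is the schedule of the Neuropathy Total Symptom Score: Section 2 gives baseline and 12 months, while Table 1 also marks screening and month 6. Its model follows from whichever schedule is confirmed.
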